Longitudinal resting images will be acquired before inflation. Blood flow estimated by the pulsed Doppler velocity signal using the outer envelope technique to calculate the velocity time integral will be obtained from a mid-artery sample volume at baseline and upon immediate cuff release to assess hyperemic velocity. Peak hyperemic velocity will be determined from the first complete velocity envelope after cuff release. Higher values of hyperemic velocity represent better microvascular dilatation ⁹³. Longitudinal images of the artery in B mode will be continuously recorded for 3 min after cuff deflation. Images will be recorded digitally using an R-wave gated digitizing interface external to the machine (MIA- LLC, Coralville, IA).

A few minutes after deflation, another image will be acquired to reflect a reestablished baseline. The above procedure is repeated to acquire the images in

deviation of 0.93% and between-subject standard deviation of 1.77%. Thus, the test-retest coefficient of variation was 7.2% in our laboratory.

Biomarker measurements

We may use specimen collected as part of this study for analysis of DNA which may include whole genome sequencing. Plasma endothelin-1 will be measured using validated ELISA kits (R&D systems, Inc., Minneapolis, MN). 24h urinary nitrite and nitrate and total nitrates will be measured using the Greiss reaction using kits from R&D systems, Inc. Renin and aldosterone will be measured using a commercial laboratory (LabCorp, Burlington, NC). Plasma ADMA will be measured using LCMS in our biochemistry core lab. The usual labs such as blood counts, chemistries, urine albumin and Na will be measured in the hospital laboratory. Renin + aldosterone lab testing will require the participants to be resting in seated position for at least 15 minutes prior to blood draw.

STATISTICAL METHODS

Outcome Variables

The outcome variables are as follows:

1. Change from baseline to 12 weeks in diastolic BP in EPO treated patients compared to delayed start controls. In the waitlisted group, we will measure the change from 12 weeks to 24 weeks compared to the change from 0 to 12 weeks.
2. Change from baseline to 12 weeks in systolic BP in the comparisons above. Between group change in hypertension status from baseline to 12 weeks. Worsening of hypertension at any time point will be defined either as an increase in BP medication or an increase in seated clinic diastolic BP of ≥ 10 mmHg or systolic BP ≥ 20 mmHg. Within-group change in hypertension status from 12w to 24 w will be compared to the control period of 0 to 12w in the delayed start group.
3. The primary outcome variable in this aim is to examine the change in FMD from baseline to 4 weeks in those treated with EPO compared to the waitlisted group. The hypothesis being tested is that EPO will cause impairment in endothelial function. Accordingly, those on EPO will have worsening of FMD.
4. The primary outcome variable in this aim is to examine the predictors of change in FMD from baseline to 4 w in those treated with EPO compared to time controls. Predictors of this change will be baseline values of the following variables: ADMA, urine nitrate and nitrite, renin, aldosterone, and plasma endothelin-1 and change from baseline to 4 w in the above variables. This analysis will answer the question: which of the pathways independently is predictive of endothelial dysfunction?

Sample Size

The primary objective of the study is to assess the change from baseline to 12 weeks in diastolic BP in EPO treated patients compared to controls. In the waitlisted group, we will measure the change from 12 weeks to 24 weeks compared to the change from 0 to 12 weeks. We have measured 24h

ambulatory BP in 183 CKD patients 4 weeks apart. The mean diastolic BP at baseline was 68.3 mmHg and at 4 weeks 68.1 mmHg. The mean difference was 0.14 mmHg and the standard deviation of the difference was 10.3 mmHg. With these assumptions, two-tailed tests and 80% power, the required sample size to detect a between-group difference of 5 mmHg is 68 subjects completing the study in each group. Assuming 85% of those randomized complete the trial, we would need to randomize $68/0.85 = 80$ subjects per group, or 160 subjects in total.

The standard deviation of the difference in systolic BP is 16.7 mmHg and we can detect an 8.4 mmHg between-group difference using the above assumption. The assessment of endothelial function is another major goal of this application. Position papers on FMD studies 90 state the following: "Typically, significant improvement in FMD can be seen with 20 to 30 patients in a crossover design study and 40 to 60 patients in a parallel-group design study. In studies of this size, the minimal statistically significant improvement that can be detected with intervention is an absolute change in FMD of 1.5% to 2%." The SD of absolute change within subjects in our lab is 0.93%. The sample size proposed (160) will allow us to detect a change of as little as 0.45%. Notably, this change is much more sensitive—approximately one quarter of what is commonly seen with typical sample sizes in conventional FMD studies.

Analysis

The analyses will begin with descriptive statistics. Overall and by-group descriptive statistics will be calculated and examined graphically. Tests for differences in demographics between the early and delayed start groups and characteristics of dropouts will be computed using t-tests, chi square (or Fisher's exact tests if $n < 6$ per cell) to understand if potential differences exist, although such differences are not expected. Comparison of the three UACR strata will be done to assess if there are differences in the populations recruited. Randomization will be within UACR group so that these differences should not bias the trial.

Primary Analysis

To test the hypothesis that early start EPO will worsen the 24-hour DBP assessed by change from baseline to 12 weeks, a mixed model will be used to analyze the results.

We will fit two separate models:

- model 1: The outcome variable will be 24h ambulatory diastolic BP. The predictors will be indicator variables for group (early or late start), time (baseline and 12 weeks), stratum (UACR: none, high, very high) and all interactions. The random component of the mixed model will include subject and time. Unstructured covariance will be used with estimation of marginal means by maximum likelihood. We expect the interaction between group by time to be significant. The random coefficient analysis does not require baseline systolic BP as a covariate. If the 3-way interaction term (group x time x stratum) is significant, then results will be reported within each stratum. Confirmatory analyses will utilize change from baseline in clinic diastolic BP.
- model 2: The outcome variable will be 24h ambulatory diastolic BP. The predictors will be indicator variables for period within the delayed start group (early or late), time (baseline and 12 weeks from start of period), stratum (UACR: none, high, very high) and

all their interactions. The random component of the mixed model will include subject and time. We expect the interaction between period by time to be significant. If the 3-way interaction term is significant, then results will be reported within each stratum.

Accounting for missing data

Ambulatory BP recording, the gold-standard to assess BP, is carried out only twice during the trial in the parallel group analysis, but clinic BP measurements occur every 4 weeks. Patients who drop out but have some post-baseline measurements of clinic BP will be included in the analyses, thus minimizing loss to follow up. We will impute ambulatory BP as follows: we will use the complete data to build a model that relates the follow-up mean 24-hour ambulatory diastolic BP from the baseline 24-hour ambulatory diastolic BP and the clinic measures using repeated measures Mixed Model regression - then use the expected value from the model for the missing value - and use PROC MI (which generates maybe 5 replicate values to insert variability into the imputation) so that there is a price to pay for imputing.

Comparison of the cohort with these measurements will also be done to understand if the inferences based on the ambulatory BPs accurately reflect the differences between the treatment groups using the clinic BPs. Repeated measures mixed models (PROC MIXED in SAS) will be utilized to assess the overall differences between the treatment groups using the clinic BPs. Additional analyses will explore the nocturnal patterns between the groups in the ambulatory BPs as well as the pattern over time using circadian models of BP in each group.

Between-group changes in hypertension status from baseline to 12 weeks will be tested using logistic regression. Worsening of hypertension at any time point will be defined either as an increase in BP medication or an increase in seated clinic diastolic BP of ≥ 10 mmHg or systolic BP ≥ 20 mmHg. The McNemar test will be used to compare within-group change in hypertension status from 12w to 24 w to that in the control period of 0 to 12w.

To test the hypothesis that EPO is causal to EIH via worsening of FMD, we will evaluate changes from baseline in FMD. That is, we will test if the worsening is a mediation effect using the technique described by Judd and Kenny⁹⁶ and elaborated by MacKinnon⁹⁷. The technique, expanded here for more than one potential mediator employs three regression equations:

- A. $Y = \beta_0 + \tau X_p + \varepsilon$
- B. $X_i = \beta_0 + \alpha_i X_p + \varepsilon$
- C. $Y = \beta_0 + \tau' X_p + \beta_1 X_1 + \dots + \beta_i X_i + \dots + \beta_k X_k + \varepsilon$ for all mediators together,
or $Y = \beta_0 + \tau' X_p + \beta_i X_i \varepsilon$ for each mediator separately

Y is the outcome result (e.g., change in 24-hour diastolic systolic BP), X_p is the group (early vs delayed start) and X_i represent the k purported mediators. The total effect of the treatment on the outcome (measured by the coefficient, τ) is the sum of direct effect (τ') of the treatment and the mediated, or indirect, effects ($\alpha_i \beta_i$). Mediation is established when four conclusions are met: (1) the treatment predicts the outcome variable (supported by a test of statistical significance of τ in equation [A]); (2) the treatment causes the potential mediator (α_i is significant in [B]); (3) the mediator causes the

outcome variable controlling for the group assignment (β_i is significant in [C] and $\tau' < \tau$, which provides evidence for mediation rather than suppression); and (4) the mediated effect is statistically significant. For mediators that satisfy conclusions 1 through 3, the significance of mediation (conclusion 4) will be determined via interval estimation of the mediated effect using the asymptotic variance derivation of Sobel ⁹⁸ since the outcomes are the continuous measures. Additional analyses that look at thresholds of change (binary: worsening of hypertension or not) will utilize bootstrapping methods and logistic regression. The proportion of the effect mediated is calculated as the ratio of the indirect effect to the total effect, or $\alpha\beta/\tau$.

The primary outcome for flow-mediated dilatation is change in FMD from baseline to 4 w in those treated with EPO compared to time controls. Predictors of this change will be baseline values of the following biomarkers: plasma ADMA, urine nitrate and nitrite, and plasma renin, aldosterone, and endothelin-1 and change from baseline to 4 w in the above biomarkers. In addition, the baseline FMD will be an independent variable. This analysis will use regression models similar to the above-listed analyses.

Pre-specified sub-group analyses for BP response

- Effect of age: The effect of age (e.g., 65 or more and <65) will be tested using interaction effects.
- Effect of volume overload: Volume overloaded subjects are more likely to show worsening EIH with EPO therapy. In people with volume overload, renin and aldosterone levels are expected to be low and 24-hour urine Na high. We will dichotomize the baseline levels of these markers and examine the outcome on ambulatory BP using interaction effects.

Safety analysis

The number of subjects who experience hypokalemia, hypercalcemia, gout, hospitalization for diabetes mellitus, transient elevations in serum creatinine concentration, and symptomatic orthostatic hypotension will be counted for each group and compared using a Poisson regression model using terms for treatment and treatment x stratum. The statistical significance of the treatment term will be used to indicate differences between CTD and placebo. If the interaction term is significant then the event rates will be reported for each stratum. The mean change from baseline in serum potassium, calcium, estimated GFR, uric acid, HgbA1C, PTH intact, and orthostatic BP will be calculated using mixed models as noted above.

Alternative study design considerations and clarifications

Choice of non-dialysis patients. Dialysis patients are challenging to study because it is more difficult to determine hypertension due to confounding by dry weight. Angioaccess makes it difficult to perform FMD. Furthermore, the number of dialysis patients—in contrast to CKD patients not on dialysis—is limited.

Timetable/Milestones

We expect to recruit and randomize a total of 160 participants in the first 3.5 years and complete the study in 4 years. This will require approximately 1 participant to be randomized per week. See table below.

Table 1: Timeline for randomization in the trial (t = 4y, n = 160)

	Year 1				Year 2				Year 3				Year 4			
Quarter	1	2	3	4	1	2	3	4	1	2	3	4	1	2	3	4
Patients	x	16	16	16	16	12	12	12	12	10	10	10	10	8	x	x

Feasibility

A feasibility assessment was performed using data from the Veterans Administration's Corporate Data Warehouse (CDW), a national repository of data compiled from the electronic medical record (EMR) system used by the Veterans Health Administration (VHA). These data include current and historical values from multiple domains such as patient medications, vitals, labs, procedures, and diagnoses, and are available from October 1st, 1999 forward. Of note, these data are updated on a daily basis and are neither filtered nor validated prior to entry into the CDW. We will use these values to screen potentially eligible participants. It is only possible to uniquely identify potential participants by accessing their EMRs using real social security numbers.

To determine the number of prospective subjects meeting eligibility criteria for the study, a query of all patients seen at the Roudebush VA Medical Center (VAMC) in Indianapolis was performed by the VA Informatics and Computing Infrastructure (VINCI) staff. The query sought to identify adults (at least 18 years of age) seen at the Roudebush VAMC in the past 4 weeks with CKD 3-4 (eGFR 15-60 mg/dL/1.73m²), anemia (Hgb 8-10 g/dL), and controlled clinic BP (<140/90) without receipt of an erythropoiesis-stimulating agent (ESA) within the past 12 weeks. The initial query returned 140 eligible prospective subjects. The following month, the same query returned 28 new eligible prospective subjects.

It is estimated that approximately 25% of eligible prospective subjects will consent to the study visits and, of these, 67% will randomize to the treatment (e.g., early vs. delayed start of EPO). Since we require ambulatory BP monitoring as an inclusion to participate in the trial, we expect approximately 33% of the patients to fail this criterion. After a robust recruitment in the early quarters, we expect the number of eligible participants to drop and therefore we expect fewer patients in the later quarters. Extrapolating from the feasibility data, we project that recruitment will begin in the second quarter of the first year and end by the third quarter of the fourth year from receipt of the grant, which gives us the following table.

Data and safety monitoring plan (DSMP)

We have prepared a DSMP to specify the process by which the PI will review the progress of the trial and the safety of its participants. Periodic assessments of these data will be done in addition to mandatory reporting requirements of the IRB

REFERENCE LIST

2. van de BP, Tielemans C, Vanherweghem JL, Degaute JP. Effect of recombinant human erythropoietin therapy on ambulatory blood pressure and heart rate in chronic haemodialysis patients. *Nephrol Dial Transplant* 1992;7(1):45-49.
(<http://www.ncbi.nlm.nih.gov/pubmed/1316580>).
3. Anonymous. Effect of recombinant human erythropoietin therapy on blood pressure in hemodialysis patients. Canadian Erythropoietin Study Group. *Am J Nephrol* 1991;11(1):23-26.

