EPO, through its receptors on the endothelial cells, especially in the setting of CKD, can trigger endothelial dysfunction and vasoconstriction. The nitric oxide pathway is severely deranged in response to EPO.; ADMA concentrations increase and cGMP release with NO-donors is impaired. Inhibitors of NO synthase severely elevate BP and provoke mortality in rodents with excess EPO expression. NO can also trigger endothelin-1 release, which itself is a potent vasoconstrictor. Prostanoids are downstream to endothelin and there is a net imbalance favoring vasoconstriction. The effects on the renin-angiotensin system are complex, but in preliminary studies vasoconstriction is to angiotensin II is enhanced when patients are given EPO. Similarly, compared to patients not on EPO, vasoconstriction to catecholamines is enhanced when patients are treated with EPO.

Endothelin-1(ET-1)

In rats with CKD, increased ET-1 expression is seen in the aorta, mesenteric artery, and renal cortex ^{45,46}. In addition, they have increased 24h urinary excretion of ET-1 ⁴⁷. EPO induces release of ET-1 from endothelial cells in culture ^{29,48}. The expression of ET-1 provoked by EPO is organ-specific. CKD rats treated with EPO have no increase in ET-1 in the mesenteric artery or renal cortex, yet the aortic content of ET-1 is increased ^{49,50}. The increase in aortic ET-1 is further augmented by the nitric oxide synthase inhibitor L-NAME, indicating that nitric oxide is an upstream process ⁴⁹. Tempol, an oxidative stress inhibitor, reduces tissue levels of ET-1, indicating that it is also an upstream process ⁵¹. However, prostanoids are downstream to ET-1 as discussed in **Figure 1**. The critical importance of endothelial expression of ET-1 is demonstrated in mice specifically overexpressing ET-1 in the endothelium. These

mice, when treated with EPO—even without nephrectomy—have impairment of endothelial function, resistance artery remodeling, aortic inflammation, and an increase in BP⁵².

Compared to wild-type mice, those heterozygous for the ETB receptor have a greater increment in BP with EPO⁵³; mice heterozygous for the ETA receptor have BP responses that are similar to those of wild-type mice. In rats with subtotal nephrectomy and EIH, treatment with a selective ETA receptor antagonist is more effective than placebo in abrogating the rise in BP⁵⁴. In contrast, the non-selective ETA / ETB receptor antagonist bosentan had no effect in preventing EIH⁵⁴.

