Endothelium: In uremia, NO synthesis in the endothelium is blunted. In vivo studies reveal that, compared to saline-treated controls, Balb/c mice with intact kidneys injected with clinically relevant doses of EPO (such as 30 U every other day for 10 weeks) showed 46% higher ADMA concentrations⁶⁴. In comparison, symmetric dimethyl arginine (SDMA) concentrations were unchanged. Of note, there is no mechanism of direct synthesis of ADMA; free ADMA is generated by proteolysis of methylated

proteins⁶⁵. Free ADMA can inhibit endothelial cell NOS and cause endothelial dysfunction and has been linked to poor outcomes in CKD.

Blood vessels: Among rats with CKD, in aortic rings, the release of cyclic GMP by nitrate donors is augmented. However, this augmentation is blunted when rats are treated with EPO⁶⁶. Among rats with CKD, in the aorta, the endothelial and inducible NO synthase protein mass is reduced regardless of EPO treatment, but when treated with felodipine the protein mass is restored, suggesting an upstream role of calcium channels.

Kidney effects: Rats with intact renal mass upon treatment with EPO display an increase in renal NO; this is noted by an increase in urinary cyclic GMP⁶⁷ and urinary nitrates⁶⁸. Rats with CKD have a reduction in urinary nitrate excretion rate that is further reduced with EPO treatment⁶⁹.

Blood pressure effects: Inhibitors of NO synthase can exacerbate hypertension in EPO-treated animals even when the renal mass is not reduced⁶⁷. The critical importance of NO in EIH has been studied in a transgenic mouse model⁷⁰. Transgenic mice overexpressing human EPO have hematocrit levels of 80%. Despite such a high hematocrit, adult transgenic mice did not develop hypertension or thromboembolism because of a compensatory increase in endothelial NO synthase levels and NO-mediated endothelium-dependent vasodilatation. Administration of L-NAME provokes vasoconstriction, an increase in vascular resistance, hypertension, and death in transgenic mice; their wild-type siblings developed hypertension but did not show increased mortality.

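### The regression meant to show which pathway independently predicts the 4-week FMD change omits baseline eGFR, so confounding by kidney function is plausible and cheaply reduced

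*Combined protocol and SAP*

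**What the plan says.** Under Outcome Variables, item 4, the aim is to learn "which of the pathways independently is predictive of endothelial dysfunction". The Analysis section gives the model: "Predictors of this change will be baseline values of the following biomarkers: plasma ADMA, urine nitrate and nitrite, and plasma renin, aldosterone, and endothelin-1", plus the changes in these markers from baseline to week 4. It then says "In addition, the baseline FMD will be an independent variable" and "This analysis will use regression models similar to the above-listed analyses".

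The analyses listed above it are of two main kinds. The mixed models contain group or period, time, UACR stratum and their interactions. The mediation equations contain treatment group and mediators only: "X_p is the group (early vs delayed start) and X_i represent the k purported mediators". Neither kind includes eGFR. Elsewhere, eGFR serves as an eligibility criterion, a screening laboratory test, a harms measure and a safety outcome. The visit table in Figure 2 schedules blood labs, including a renal panel, at baseline and every 4 weeks.

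On the biology, the Background section on molecular mechanisms says "EPO, through its receptors on the endothelial cells, especially in the setting of CKD, can trigger endothelial dysfunction and vasoconstriction". It reports raised endothelin-1 expression in rats with CKD and blunted endothelial nitric oxide synthesis in uremia. It also says "Rats with CKD have a reduction in urinary nitrate excretion rate that is further reduced with EPO treatment".

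**The concern.** To call a pathway independently predictive is to say more than that it correlates with the FMD change. If kidney function influences both a marker and the FMD response, the marker's coefficient carries part of the kidney effect unless kidney function is in the model. Randomization protects the group terms (τ and α in the mediation equations). It does not protect the biomarker coefficients in the FMD regression or the β terms in equation C, which are observational associations among patients.

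At stake is the mechanistic conclusion, which is the trial's stated purpose. Severity of CKD could be reported as a molecular pathway of EPO-related endothelial dysfunction, or a real marker effect could be hidden.

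**Working it through.** **1. The plan's own number.** No power calculation is given for the biomarker regression, so its size has to come from the main calculation. With SD 10.3 mmHg, a difference of 5 mmHg, 80% power and two-sided testing (α is not stated; 0.05 assumed): 2 × (1.960 + 0.842)² × 10.3² / 5² = 66.6 per group by the normal approximation, and 67.6 by the t distribution, hence 68. Then 68 / 0.85 = 80 randomized per group. The plan's figures reproduce. Completers total 2 × 68 = 136.

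**2. Where eGFR could enter.** The explicit terms in the FMD regression are the markers, their changes and baseline FMD. The reference to similar models could bring in group and UACR stratum. It cannot bring in eGFR, because no earlier model contains it.

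**3. Size, under assumed correlations.** Let r₁ be the correlation of one baseline marker with eGFR, and r₂ that of eGFR with the FMD change. Give the marker no effect of its own.

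- eGFR acts in both arms: the marker's test statistic is shifted by about δ = r₁ × r₂ × √136, where √136 = 11.66.
- eGFR acts only in treated patients: with 1:1 allocation the average slope is halved, so δ is halved.
- False-positive rate = P(Z > 1.96 − δ) + P(Z < −1.96 − δ).

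| r₁ / r₂ | δ, both arms | Formula | Simulated | δ, treated only | Formula | Simulated |
|---|---|---|---|---|---|---|
| 0.2 / 0.2 | 0.47 | 8% | 7-8% | 0.23 | 6% | about 5% |
| 0.3 / 0.2 | 0.70 | 11% | 10-12% | 0.35 | 6% | 6% |
| 0.5 / 0.3 | 1.75 | 42% | 39-43% | 0.87 | 14% | 14% |
| 0.6 / 0.4 | 2.80 | 80% | 75-78% | 1.40 | 29% | 27-28% |

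The simulated columns come from least-squares regressions at n = 136 with 2,000 or more trials per setting. Most used the full predictor list (group, baseline FMD, five baseline markers, five changes); some used a shorter one. With eGFR added, the rate is about 5%.

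**4. Does UACR stratum do the job?** Assuming a correlation of 0.4 between UACR and eGFR, and an effect in both arms, adding the three strata lowers the rate from 7% to 6% (0.2 / 0.2), 19% to 14% (0.3 / 0.3), 43% to 33% (0.5 / 0.3) and 65% to 55% (0.5 / 0.4). It removes only part of the bias.

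**5. Which terms are exposed.** Baseline marker levels are the most exposed. A change score removes any stable effect of eGFR on the marker's level. In mediation equation B the regressor is the randomized group, so α is already protected. In equation C, β is not.

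**The case against.** The strongest objection is to the premise. The cited experiments mostly contrast animals with and without CKD. Everyone enrolled is meant to have CKD, so restriction removes that contrast, and no section reports a gradient of any marker or of FMD across eGFR within stage 3-4. A reader might infer that the plan itself names kidney function as a common cause of all the biomarkers and of the outcome. The documents do not say that. Their support covers endothelin-1 and the nitric oxide pathway, and the endothelin evidence is rat tissue expression and urinary excretion, whereas the trial measures plasma. For ADMA they give a link to outcomes in CKD and a rise with EPO in mice with intact kidneys. For renin and aldosterone they state no CKD effect. They also report endothelial impairment with EPO in non-nephrectomized mice that overexpress endothelin-1. All of this stands, and it limits the claim to plausibility.

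The second objection also stands. The background sentence says CKD strengthens the response to EPO, which describes treated patients. On that reading the lower set of rates applies, and at weak correlations almost nothing is lost.

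A third objection is that independently may mean independent of the other pathways, which joint entry provides, and that this work is described as exploratory. That is a fair reading. But joint entry of markers that share a cause does not remove that cause, and the term will be read more widely once reported.

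**Conclusion.** The omission is plain in the text, and the confounding is plausible but not demonstrated. For one inert marker, the chance of a false independent finding is about 8% to 78% if eGFR acts in both arms, and about 5% to 27% if it acts only in treated patients, against about 5% with eGFR in the model. These ranges rest on assumed correlations (0.2 to 0.6 and 0.2 to 0.4), 136 completers and a two-sided 5% level per term.

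Two stronger readings should be resisted. The first is that several pathways are likely to be false. With all five markers correlated with eGFR at 0.3 / 0.3, at least one is falsely called in 47% of simulated trials (both arms) or 28% (treated only). About 20% to 22% remains with eGFR in the model, from testing five markers, and the documents give no basis for supposing that all five are affected. The second is that the main result is at risk. The 24-hour diastolic BP comparison rests on randomized groups and is not affected.

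**What to change.** In the FMD-change regression, pre-specify baseline eGFR as a continuous covariate together with UACR stratum. Do the same in mediation equation C whenever biomarkers are entered; the plan names FMD as the mediator, but the equations are written for several. Equation B does not need eGFR to remove bias. Use the words independently predictive only for results from the adjusted model, and report the unadjusted model beside it.

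Keep the change in eGFR to week 4 for a sensitivity analysis. It is measured after randomization and may itself respond to EPO or BP, so adjusting for it in the main model could remove part of the effect under study.

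The cost is a few lines in the SAP. With an intercept, group, baseline FMD, five baseline markers and five changes, the model has 13 parameters and 136 − 13 = 123 residual degrees of freedom. eGFR takes one and the three-level stratum two, leaving 120. No new data are needed and the sample size is unchanged.
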